9.3 Symptomatic Treatment for Apatinib-Related Adverse Reactions

1) Hand-and-foot syndrome (HFS)

Hand-and-foot syndrome is skin toxicity with palmar-plantar dysesthesia or acral erythema and manifests especially in areas under pressure or force. It may occur in patients with tumor during chemotherapy or molecular targeted therapy. HFSR is characterized by numbness, dysesthesia, paraesthesia, tingling, no pain or pain, skin swelling, or erythema, desquamation, chapping, scleroma-like blisters, and severe pain.

HFS grading:

Grade 1: numbness/dysesthesia/paraesthesia, painless swelling or erythema of the hands and/or feet and/or discomforts that does not affect normal activities.

Grade 2: painful erythema and swelling of the hands and/or feet and/or discomforts affecting patients' activities of daily living.

Grade 3: wet desquamation, ulcers, blisters, or severe pain of hands and/or feet and/or severe discomforts that causes the patients to be unable to work or perform activities of daily living. Intense pain and loss of skin function, relatively rare.

Symptomatic treatment and management of HFS:

Some necessary symptomatic and supportive treatments must be taken, including: strengthen skin care, keep skin clean, and avoid secondary infections; avoid pressure or friction; use moisturizers or lubricants, topically use lotions or lubricants containing urea and corticosteroids; topically use antifungal or antibiotic treatment if necessary.

Note: If Grade 3 or greater HFS occurs for more than 3 times with an aggravating trend, the subject should discontinue the study treatment and withdraw from the study.

2) Hypertension

Patients should be strictly screened according to blood pressure requirements in the inclusion and exclusion criteria prior to enrollment. Patients with hypertension can control the blood pressure by adjusting the dose of or adding new antihypertensive drugs before administering the study drug. The blood pressure must be under 140/90 mmHg (average of 2 blood pressure measurements taken at least 24 h apart) before randomization.

Monitoring and handling of such hypertension: Blood pressure should be monitored at least 3 times a week during the first 2 cycles of the targeted pharmacological treatment.

If hypertension occurs or aggravates during the administration, 1) give or adjust the dose of antihypertensive drugs, and 2) adjust the study drug as per the study protocol.

If any arterial thrombosis (such as cerebral ischemia, stroke, angina pectoris, myocardial infarction, etc.) occurs, the subject should discontinue the treatment immediately and withdraw from the study. In the case of any symptomatic IV venous thrombosis, the subject should discontinue the treatment and withdraw from the study.

Once the symptoms of thrombosis are observed, symptomatic treatment, surgery, or anticoagulants shall be immediately given.

6) Reversible posterior leukoencephalopathy syndrome

Reversible posterior leukoencephalopathy syndrome has not been reported in completed clinical studies of apatinib, but has been found in clinical application of newly marketed anti-angiogenic macromolecular antibodies and small molecule inhibitors.

The clinical manifestations are headache, altered consciousness/confusion, abnormal vision/blindness, and convulsion, often accompanied by hypertension. The causes of reversible posterior leukoencephalopathy syndrome are yet unidentified. Once the symptoms are suspected, the study drug should be discontinued immediately, and symptomatic treatment and strict blood pressure control should be given. The subject will withdraw from the study once the imaging diagnosis is confirmed.

7) Fatigue and weakness

Fatigue and weakness are common tumor-related clinical symptoms, the cause of which might be electrolyte disturbance, abnormal liver function, abnormal cardiac function, etc. Also, fatigue and weakness are common adverse reactions of targeted anti-angiogenic drugs, such as sunitinib, pazopanib, and sorafenib. Clinical reports show that targeted anti-angiogenic drugs may increase the incidence of fatigue and weakness through hypothyroidism.

In previously completed clinical studies of apatinib, subjects in the treatment group showed a higher incidence of fatigue and weakness than those in the control group, and the mechanism behind the increased incidence of fatigue and weakness caused by apatinib is yet unidentified.

Therefore, close attention should be paid when a patient show and report Grade 2 or greater fatigue and weakness. In the case of Grade 3 or greater fatigue and weakness, the patient should be admitted to the hospital immediately for detailed examinations to exclude possible reasons such as electrolyte disturbance, abnormal liver function, cardiac dysfunction (ECG, echocardiography), and abnormal hormone levels (adrenal hormones, thyroid hormones). A symptomatic treatment should be given and the dose should be interrupted or modified according to the principle of dose modification.

8) Abdominal pain

Abdominal pain is not uncommon in the treatment of lung cancer with apatinib, which are mostly a concomitant symptom of tumor. Also, gastrointestinal perforation occasionally occurs in clinical studies of apatinib and other anti-angiogenic drugs. For subjects with abdominal pain, the investigator should be cautious of potential gastrointestinal perforation. Upon the observation of gastrointestinal perforation, the drug should be discontinued immediately, and the subject should withdraw from the study and be given an active symptomatic treatment.

9) Interstitial pulmonary fibrosis

The clinical physicians should fully understand the conditions of subjects and be familiar with the drugs that may lead to pulmonary toxicity. The clinical symptoms and changes in chest X-ray or CT should be closely monitored. Once cough, chest tightness, labored breathing, dyspnea, and hemoptysis of unknown causes, the drug should be discontinued as soon as other causes (such as infection and heart failure) are ruled out. Alveolar lavage fluid analysis and surgical lung biopsy are important means to diagnose interstitial lung disease. Currently, no therapy yields a satisfactory therapeutic effect on pulmonary fibrosis, and correction of hypoxemia and timely administration of corticosteroids are recommended following "Guidelines for Diagnosis and Treatment of Idiopathic Pulmonary (Interstitial) Fibrosis" issued by the Chinese Medical Association Respiratory Diseases Branch.

Note: Consult specialists when necessary.

10 EFFICACY EVALUATION

The objective response rate (ORR), duration of response (DoR), clinical benefit rate (CBR), time to response, progression-free survival (PFS), 12-month survival, and overall survival (OS) will be evaluated.

The tumor imaging assessment will be performed once every 2 cycles (8 weeks) based on RECIST v1.1 (Appendix V). For subjects with CR/PR for the first time, the results should be confirmed after 4 weeks. The tumor assessment will be carried out once every 3 cycles (12 weeks) 6 months after the first dose of the drug.

Imaging results (including MRI and CT) of all subjects should be confirmed by blinded independent imaging experts. Subjects with efficacy evaluation results of CR, PR, SD, and PD should first be reviewed by the Principal Investigator (PI) of each study site, with all imaging results of response evaluation saved and finally collectively and independently assessed and confirmed by imaging experts.

11 STUDY MANAGEMENT

11.1 Ethics and Informed Consent

This clinical study must comply with the "Declaration of Helsinki (1996)", NMPA's "Good Clinical Practice (GCP)" and relevant regulations. The study can only be initiated after obtaining the approval from the IRB/IEC. During the study, amendments to this study protocol must be reported to the IRB/IEC and be archived.

The clinical investigator must follow all applicable laws and regulations to protect the subjects. The informed consent form used in the informed consent process must be approved by the IRB/IEC and be readily available for inspection.

The clinical investigator must inform subjects that participation in the clinical study is voluntary and that they have the right to withdraw from the study without being discriminated or retaliated, and their medical treatment and right will not be affected, and they can continue to receive other therapies. All subjects should be informed that the participation of the study and their personal information will be kept confidential. Also, the subjects should be informed of the nature, objectives, expected potential benefits, and possible risks and inconvenience of the clinical study, other alternative treatment options, and rights and obligations of the subjects in accordance with the "Declaration of Helsinki". Subjects should be given sufficient time to consider whether to participate in the study and sign the informed consent form.

Before the implementation of any process required by the study protocol, the subjects must:

- Be informed of information relevant to the study and all content and terms in the informed consent form.
- Be given sufficient time to ask questions and consider whether to participate in the study.
- Be enrolled in the study voluntarily.
- Sign and date the informed consent form approved by the IRB/IEC.

In the case of major changes during the study, the protocol should be amended. Unless it is necessary to eliminate obvious direct harms to subjects, the investigator must not make any change to the study without the approval of the IRB/IEC and sponsor. Changes to the study protocol intended to eliminate obvious direct risks to subjects can be implemented immediately, but the changes must be recorded in protocol amendments, reported to the IRB/IEC, and submitted to relevant regulatory authorities within a required period. The process of protocol amendment must follow the same process of review and approval of the original protocol.

11.2 Protocol Amendments

The "Clinical Study Protocol" and "Clinical Study Case Report Form" are formulated by the PI, agreed upon by Hengrui, which is the study sponsor and study drug provider, and approved by the Ethics Committee of the hospital before implementation. During the clinical study, any changes to the study protocol must be discussed with Hengrui, and approved by the Ethics Committee.

11.3 Quality Assurance of Clinical Study

To ensure the quality of the study, the sponsor and PI will jointly discuss and formulate a clinical study plan before the formal study initiation. All the relevant study staff in the clinical study shall be trained for the study protocol and GCP.

The study drug in the clinical study shall be managed in accordance with the SOP, including receiving, storage, dispensing, and returning.

Hengrui may conduct monitoring and auditing on the request of the PI. The CRA shall follow the GCP and SOP, make visits to the study site for clinical monitoring on a regular basis or according to the actual conditions, supervise the implementation and progress of the clinical study, check and confirm that all data recorded are correct and intact and are consistent with source data, and ensure that the clinical study is implemented following the study protocol. The investigator should cooperate with the monitor actively.

According to the GCP guidelines, necessary measures shall be taken at the design and implementation stages of the study to ensure that all collected data are accurate, consistent, intact, and reliable. All observed results and abnormal findings in the clinical study must be verified and recorded in a timely and serious manner to ensure data reliability. All instruments, equipment, reagents, and standards used in various tests in the clinical study must have stringent specifications and be operated under normal conditions.

11.4 Data Management

Data management is to ensure the reliability, integrity, and accuracy of the data, with an objective to obtain authentic data of high quality for statistical analysis.

Data will be collected and managed using the electronic case report form (eCRF).

11.4.1 Data collection

Data will be collected using the eCRF. Jiangsu Hengrui Pharmaceuticals Co., Ltd. will provide an electronic data capture (EDC) system. Company staff will deliver EDC system training to the designated staff of study site. Access to EDC system will only be granted to the study site staff who have completed the training. The PI or dedicated data entry person (CRC) should input data into the EDC system in accordance with the requirements of the visit procedures and the eCRF completion guide. The logic verification program in the system will verify the integrity and logic of the clinical study data entered into the EDC system and generate an error message prompt for questionable data. The PI or CRC is permitted to modify or explain the problematic data. After the database is locked, the investigator will receive a CD-ROM or copy of subject data to archive at the study site.

Hengrui is the sole owner of all original eCRFs. Aside from Hengrui or the representatives from regulatory authorities, no one is allowed to provide any data to a third party. The investigator is ultimately responsible for collection and report of all clinical and laboratory data recorded in eCRFs and other data collection forms (source records) to ensure the attributability, legibility, timeliness, primitiveness, accuracy, durability, integrity, and consistency of the data.

Signature of the investigator or authorized personnel must sign to confirm the authenticity of the data in eCRFs. Any data correction in source record or eCRF should be dated, signed, and given with necessary explanations. Source data cannot be covered.

Source records are usually graphs from a hospital or a physician, In this case, the data collected in the eCRF must be consistent with those in the graph. An eCRF can be used as a source record under certain circumstances. The study site is required to provide documents to clarify the data that should be recorded in eCRF and to use the eCRF as a source record.

11.4.2 Data management and quality control

To ensure authenticity and reliability and improve the quality of the clinical data, the CRA will monitor the integrity, consistency, and accuracy of the study data in the database, and guide the study site staff to add or correct the data whenever necessary. The CRA or data manager will send electronic query form to the PI or CRC for problematic data. The PI or CRC must respond and provide correction or explanation of the problematic data. Multiple queries may be raised when necessary until the problem is solved. The medical director and data manager should perform consistency comparison of SAEs periodically.

At the end of the study, the data manager and medical personnel will conduct a final quality control on all data in the database, summarize all protocol deviations and violations during the study, and hold a data verification meeting. Database locking and unblinding will be carried out after the quality requirements have been met. The data manager will export the data to the statistics department for data analysis.

11.4.3 Data review and study site monitoring

Before the initiation of the study, a representative from Jiangsu Hengrui Pharmaceuticals Co., Ltd. will introduce study protocol and eCRF (Part 2) to the investigator and staff at the initial visit to the study site. During the study, the CRA will visit the study center on a regular basis to monitor the integrity of the subjects' records and accuracy of the eCRF, compliance with the study protocol and GCP, and progress of the enrollment, and to ensure that the storage, dispensing, and count of the study drug are performed according to the requirements. During these visits, the major research personnel are required to assist the work of CRA.

The investigator shall keep the source documents of each subject, including all medical records and visit records (outpatient or inpatient record), such as demographic parameters, medical information, lab results, ECGs, and result of other examinations and evaluations. All information on the eCRF must come from the source documents of the subject. The investigator shall also keep the informed consent forms signed by the subjects.

The investigator must ensure that all source documents are available for monitoring to verify their consistency with the eCRF. Jiangsu Hengrui Pharmaceuticals Co., Ltd. requires to completely monitor the signed informed consent forms, compliance with inclusion/exclusion criteria, SAEs records, and all data required for evaluation of primary endpoints and safety endpoints. Additional monitoring will be performed on consistency of source data and eCRF according to monitoring plan specified by the study. No information related to subjects' identity in the source document will be disclosed.

11.4.4 Record retention

To fulfill the review and/or audit requirement of regulatory authorities or Hengrui, the investigator/study site must agree to keep all relevant records, including all subjects' ID number (with sufficient information linked to the records, such as the CRF and medical record), all original informed consent forms, all copies of the CRF, safety reports, source records, detailed treatment records, and relevant communication documents (such as letters, minutes, and telephone reports). The investigator/study site should keep the records according to related specifications.

If the study record cannot be kept for any reasons, the investigator/study site should inform Hengrui in advance. Study documents should be kept by the study site for 5 years after completion of the clinical study. Hengrui will inform the investigator/study site if the documents are no longer required to be retained.

12 DATA MANAGEMENT AND INTELLECTUAL PROPERTY RIGHTS

12.1 Data Processing

After the completion of the study, data will be processed by the data statistics company authorized by the sponsor. Inconsistency in the documents will be discovered via data verification. Any inconsistency in the documents should be clarified by the investigator through CRA. Database will be locked after the data is verified. No access is allowed without authorization. Following database locking, the statistician will unblind the data after applying with the sponsor and PI and obtaining agreement from all the three parties. To ensure the safety of the data, irrelevant personnel cannot access or modify data. Data should be backed up. Any changes to the data should be approved with written agreements by the principal investigator, statistician, and data manager before it can be changed.

12.2 Publication of Study Results

The ownership of the study results belongs to both the PI and Hengrui. Hengrui does not limit the publication of any collected or generated data by the investigator, regardless of whether the results are beneficial to the study drug. The investigator must promise that no data relevant to the study and/or study results should be published on journals and academic or commercial conferences without written permission from Hengrui, and also understand that Hengrui will not disapprove the publication without reasons.

However, the investigator should inform Hengrui in advance to review any proposed publication or other forms of release before submission or publication to prevent unintentional leakage of confidential information or unprotected inventions. The investigator should provide Hengrui with the manuscript, abstract, or full text of all planned publications (posters, invited lectures, or guest lectures) at least 30 days prior to the submission for publication or other forms of release. Hengrui will check the content according to the laws and regulations and intellectual property. To protect the intellectual property, especially before the acquisition of patent, the investigator should agree to delay or cancel the publication. Before open publication, Hengrui can require the investigator to delete any previously unpublished confidential information.

The investigator is not allowed to mention Hengrui in their promotional materials or publications before obtaining written agreement from Hengrui. In the meantime, sponsors are not allowed to use the investigator's name in promotional materials or publications before obtaining written agreement from the investigator and/or collaborator.

13 STATISTICAL ANALYSIS

13.1 Determination of Sample Size

The sample size in Stage I is primarily based on clinical considerations, and the number of subjects actually enrolled in each dose group is determined by the number of subjects who show clinically significant toxicity during the observation period for tolerability. During the expansion stage of PK study, 10-12 subjects are required for each group. The sample size in Stage I is 40-60 subjects.

In Stage II, for cohort 1, assuming that the ORR of the combination therapy is 30% with a bilateral alpha of 0.05, enrollment of 62 subjects will have a 80% power to ensure that the ORR of the combination therapy has a lower 95% CI limit of > 15%. If the dropout rate is 20%, 78 subjects should be enrolled.

For cohorts 2 and 3, assume that the ORR point estimate of each cohort is 30% and the width of the 90% confidence interval is 0.3, 38 subjects are required for each group when a 20% dropout rate is considered.

For cohort 4, assume that the ORR point estimate is 50% and the width of the 90% confidence interval is 0.4, 20 subjects are required to be enrolled.

In Stage II, the four cohorts require to enroll a total of 174 subjects.

13.2 Statistical Hypotheses

The primary endpoint in Stage II is ORR.

Null hypothesis: $ORR = 15\%$

Alternative hypothesis: $ORR \neq 15\%$

13.3 Analysis Sets

Full analysis set (FAS)

All subjects who have received at least one dose of the study drug.

Evaluable set (ES)

ES is a subset of FAS, which is defined as the subjects who have received at least one dose of the study drug, and have at least one post-baseline imaging assessment for efficacy. **Per-protocol set**

All enrolled subjects who have received at least one dose of the study drug without major protocol deviation.

Safety analysis set

All enrolled subjects who have received at least one dose of the study drug and have safety record after administration. This analysis set is used for safety analysis.

Pharmacokinetic analysis set (PKS):

1) Concentration analysis set

PK concentration analysis set is defined as the subjects who have received the study drug and have at least one blood concentration observation per cycle.

2) Parameter analysis set

PK parameter analysis set is defined as the subjects who have received the study drug and have at least one primary PK parameter per cycle. Subjects who have not completed the PK study should be excluded.

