2 STUDY OBJECTIVES AND ENDPOINTS

2.1 Study Objectives

Primary objective of Stage I study:

To evaluate the tolerability and safety of anti-PD-1 antibody SHR-1210 plus apatinib mesylate in patients with advanced NSCLC

Secondary objectives of Stage I study:

- 1) To evaluate the pharmacokinetics of anti-PD-1 antibody SHR-1210 plus apatinib mesylate in patients with advanced NSCLC
- 2) To preliminarily evaluate the efficacy of anti-PD-1 antibody SHR-1210 plus apatinib mesylate in patients with advanced NSCLC

Objectives of Stage II study:

To observe and evaluate the efficacy and safety of anti-PD-1 antibody SHR-1210 plus apatinib mesylate in patients with advanced non-small cell lung cancer

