If a subject interrupts the administration of apatinib during the period of pharmacokinetic blood sampling due to adverse events and if the interruption of apatinib occurs during C1D22-D28, the subject will not be subject to pharmacokinetic blood sampling in the future and will be deemed as not completing the pharmacokinetic study; if the interruption of apatinib occurs during C2D23-C2D28, the pharmacokinetic blood sampling will not be carried out on C2D28. Then, after the administration of apatinib is resumed and continued for 7 days, the administration of apatinib and the blood sampling will be carried out on D7 according to the administration method of apatinib (administration under fasting) and the time points of blood sampling specified for C2D28.

If the administration of SHR-1210 can not be carried out normally during C2D1-C2D28 due to adverse events, the pharmacokinetic blood sampling will not be performed starting from C2D1 and the subject will be deemed as not completing the pharmacokinetic study.

The administration of SHR-1210 should be performed at the scheduled time on C2D1 of the pharmacokinetic study, and no time window for delayed administration is set. The delayed administration of SHR-1210 on C2D15 is allowed as long as the time of administration does not exceed the planned time by more than 3 days.

Substitution of subjects is required for those who have not completed the pharmacokinetic study to ensure that 10 to 12 subjects can complete the pharmacokinetic study.

Subjects who have not completed pharmacokinetic blood sampling may continue to receive the study drug according to the investigator's judgment until an event meeting the criteria for treatment discontinuation occurs.

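### The PK parameter set drops every subject who did not complete the PK study, so valid profiles finished before an adverse event are lost and the Cmax, AUC and t1/2 summaries are conditioned on completion

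*Protocol*

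**What the plan says.** Protocol 2.1 gives as a Stage I secondary objective: "To evaluate the pharmacokinetics of anti-PD-1 antibody SHR-1210 plus apatinib mesylate in patients with advanced NSCLC". Protocol 2.2 lists the PK parameters of both drugs as Stage I secondary endpoints, and 13.4.5 summarises them by dose group.

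Protocol 13.3 defines two PK sets. The concentration set takes treated subjects who "have at least one blood concentration observation per cycle". The parameter set takes those who "have at least one primary PK parameter per cycle", and then adds: "Subjects who have not completed the PK study should be excluded". That sentence makes no exception for the reason for stopping or for profiles already measured.

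Protocol 3.2.1 defines non-completion through adverse events by two routes.

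- **Route 1, apatinib:** "if the interruption of apatinib occurs during C1D22-D28, the subject will not be subject to pharmacokinetic blood sampling in the future", and the subject is deemed a non-completer.
- **Route 2, SHR-1210 not given normally in C2D1-C2D28:** "the pharmacokinetic blood sampling will not be performed starting from C2D1 and the subject will be deemed as not completing the pharmacokinetic study".

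The same section then states: "Substitution of subjects is required for those who have not completed the pharmacokinetic study", so that 10 to 12 subjects complete.

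The SAP defines no PK set (5.1.1 and Table 1). In 5.5 it refers PK to a separate report.

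**The concern.** Membership of the parameter set depends on something that happens after many of the parameters have been measured, and that is partly driven by toxicity. Two consequences follow.

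1. **Loss of valid data.** The Cycle 1 SHR-1210 profile runs from pre-dose to 504 h and ends on D22, before the first apatinib tablet. A later apatinib interruption cannot have altered it, yet it leaves the set. A subject who cannot receive SHR-1210 on C2D1 will normally also have finished the apatinib profile started on C1D28, and that is dropped too. The groups are only 10 to 12 completers, so each such profile is worth having.

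2. **Selection.** Non-completers are replaced by subjects who do complete. If the events become more likely as exposure rises, the removed subjects tend to have higher exposure. Mean Cmax and AUC would then be too low and their spread too narrow. The protocol makes some link plausible for apatinib: section 1 reports high rates of toxicity-induced interruption and reduction at 750 mg, and 1.5.2.2 reports exposure rising with dose and marked differences between individuals. It gives no relation between exposure and toxicity within a dose.

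**Working it through.** **Step 1. Reproduce the planned number of samples.** From the time points in Protocol 3.2.1:

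| Profile | Pre-dose + post-dose | Points |
|---|---|---|
| SHR-1210, Cycle 1 D1-D22 | 1 + 8 | 9 |
| Apatinib, C1D28 | 1 + 8 | 9 |
| SHR-1210, Cycle 2 D1-D15 | 1 + 7 | 8 |
| Apatinib, C2D28 | 1 + 8 | 9 |

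9 + 9 + 8 + 9 = 35, which matches the stated total.

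**Step 2. Count what the exclusion discards per subject.**

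| Event | Profiles already complete | Points lost |
|---|---|---|
| Apatinib interrupted C1D22-D28 | SHR-1210 C1 | 9/35 = 26% |
| SHR-1210 cannot be given on C2D1 | SHR-1210 C1, apatinib C1D28 | 18/35 = 51% |
| SHR-1210 dose on C2D15 missed, 336 h sample already taken | the above and SHR-1210 C2 | up to 26/35 = 74% |

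**Step 3. Effect of replacement on numbers.** The documents give no rate of non-completion, so d is an assumption. Enrolment needed for n completers is n/(1 - d), rounded up.

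| d | for 10 completers | for 12 completers |
|---|---|---|
| 10% | 11.1, so 12 | 13.3, so 14 |
| 20% | 12.5, so 13 | 15 |
| 30% | 14.3, so 15 | 17.1, so 18 |

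For 12 completers, that is roughly 1 to 5 excluded subjects per dose group (13.3 - 12 = 1.3; 17.1 - 12 = 5.1). The planned number of completers is kept, so the loss is of additional valid profiles rather than a shortfall against plan.

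**Step 4. Illustrative bias.** All inputs here are assumptions. Exposure is lognormal, with log-scale SD s = sqrt(ln(1 + CV²)): 0.294, 0.472 and 0.632 for CV 30%, 50% and 70%. With z the standardised log exposure, the probability of non-completion is logistic in z, with odds ratio OR per SD and an intercept chosen so that the overall rate is d. The ratio of geometric means, completers to all subjects, is exp(s × mean of z among completers).

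| CV | OR per SD | d = 10% | d = 20% | d = 30% |
|---|---|---|---|---|
| any | 1 | 1.00 | 1.00 | 1.00 |
| 30% | 1.5 | 0.99 | 0.98 | 0.97 |
| 50% | 2 | 0.97 | 0.94 | 0.91 |
| 70% | 2 | 0.96 | 0.92 | 0.89 |
| 70% | 3 | 0.94 | 0.89 | 0.84 |

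The understatement runs from 0 to about 16% and exceeds 10% only toward the upper end of the assumptions.

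**Step 5. Set against sampling error.** With n = 12, the 95% CI for a geometric mean is the estimate multiplied and divided by exp(2.201 × s/√12). That gives 0.74 to 1.35 times the estimate at CV 50%, and 0.67 to 1.49 times at CV 70%. The illustrated bias lies inside the sampling error of one dose group.

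**The case against.** A reader might infer that exposure is described only in subjects who tolerated the combination. The documents do not support that. Under 3.2.1, an apatinib interruption in C2D23-C2D28 only postpones sampling until the drug has been resumed and continued for 7 days. Interruption in C2D1-C2D22 is not listed as non-completion. A C2D15 SHR-1210 dose up to 3 days late is allowed. The concentration set carries no completion exclusion, and 13.4.5 plans plots and listings for each subject.

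Other points against the concern:

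- **Not all of the loss comes from 13.3.** In route 1 sampling stops, so no apatinib profile exists. Any apatinib bias from that route arises from the sampling rule, and no redefinition of the analysis set removes it. The Step 4 figures pool all non-completion and do not show the part that could be recovered.
- **The main recoverable profile is SHR-1210 alone.** It precedes apatinib, so it is reference data for the combination objective. For SHR-1210, Protocol 1.7.1 reports no dose-limiting toxicity at any dose tested, which gives no support for exposure-driven toxicity.
- **The wording about cycles is ambiguous.** If it means every cycle, a subject stopped in C1D22-D28 has no Cycle 2 sample and fails both PK definitions even without the completion sentence. If it means cycle by cycle, the concentration set keeps the Cycle 1 data.
- **The consequence is limited.** PK is descriptive, and Protocol 3.1 bases the Stage II dose on tolerability and discussion. A completer set also suits a within-subject Cycle 1 versus Cycle 2 comparison. The separate PK report may handle the matter, but it cannot be seen.

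All of these stand as limits on size and scope. None shows that finished profiles from subjects stopped later are kept in the parameter set. That set is defined only in 13.3, which excludes them.

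**Conclusion.** The concern holds in a limited form. As written, 13.3 discards valid PK profiles because of later adverse events, and the parameter summaries are conditioned on completing the PK study, which certain adverse events prevent. The data loss, 9, 18 or up to 26 of 35 samples per excluded subject, follows directly from the documents. The third figure assumes that the 336 h sample had been taken.

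The bias is conditional. If toxicity rises with exposure, the means are somewhat too low. The documents give no non-completion rate, no CV for exposure and no exposure-toxicity relation, so the size is unknown. The 0 to 16% range is an illustration under the Step 4 assumptions, and it is zero if the two are unrelated.

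This is a cheap improvement to a descriptive Stage I secondary endpoint.

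**What to change.** In Protocol 13.3, and in the separate PK report:

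1. Define the parameter set by profile: SHR-1210 Cycle 1, apatinib C1D28, SHR-1210 Cycle 2, apatinib C2D28. A subject contributes each profile for which dosing up to that profile followed the plan and the parameter can be estimated, whether or not the PK study was completed later.
2. Delete the sentence excluding non-completers, and replace the per-cycle condition in both PK set definitions with the profile-level wording. Deleting the sentence alone may not restore the Cycle 1 data.
3. Keep the subset with all four profiles for within-subject Cycle 1 versus Cycle 2 comparisons.
4. Tabulate non-completers by reason and timing.
5. Report as a limitation that apatinib profiles never sampled after an interruption in C1D22-D28 cannot be recovered.

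This restores the Cycle 1 SHR-1210 data, and the apatinib C1D28 and SHR-1210 Cycle 2 profiles measured before a Cycle 2 event. It needs no extra subjects or samples and leaves the dosing, sampling and replacement rules as they are. The cost is a few lines of text and a number of subjects that differs between profiles, which each table should state.
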